6.4. Analyses of the Secondary Efficacy Endpoints

For the analyses of the secondary efficacy endpoints, the two-sided p-values and two-sided 95% CIs will be reported for the treatment difference between placebo arm and apremilast arm. Details for multiplicity adjustment are described in Section 6.2.

6.4.1. Binary Variables

The binary variables for secondary endpoints include the following:

- Proportion of subjects who improved ≥ 75% in BSA (BSA-75) from baseline at Week
 16
- Proportion of subjects who achieved BSA ≤ 3% for subjects with baseline BSA > 3% at Week 16
- Proportion of subjects with ≥4-point reduction (improvement) from baseline in the whole body itch NRS score at Week 16, among subjects with baseline whole body itch NRS ≥ 4
- Proportion of subjects with ScPGA score of clear (0) or almost clear (1) with at least a 2-point reduction from baseline at Week 16, among subjects with baseline ScPGA score > 2

For these binary endpoints, the treatment difference between apremilast arm and placebo arm will be compared using CMH test adjusting for the stratification factor at randomization. The two-sided p-values from the CMH test, the adjusted treatment difference in proportion using the weighted average of the treatment differences across the strata with the CMH weights, along with the associated two-sided 95% CIs using a normal approximation to the weighted average will be provided.

Missing values will be imputed using the similar MI method as the primary endpoint, with sensitivity analysis using the NRI method as described in section 6.3.

Further, analyses of the following secondary endpoints will be performed for the subjects with baseline sPGA = 2 (mild psoriasis) and sPGA = 3 (moderate psoriasis):

- Proportion of subjects who improved ≥ 75% in BSA (BSA-75) from baseline at Week
 16
- Proportion of subjects who achieved BSA ≤ 3% for subjects with baseline BSA > 3% at Week 16
- Proportion of subjects who achieved BSA ≤ 1% for subjects with baseline BSA > 1% at Week 16

The treatment difference between apremilast arm and placebo arm will be compared using Chi-squared test. The two-sided p-values from the Chi-squared test, the treatment difference in proportion, along with the associated two-sided 95% CIs will be provided.

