#### 9.6.1.2. Secondary Efficacy Endpoints

The secondary efficacy endpoints will be analyzed based on the ITT population. The two-sided p-values and two-sided 95% confidence intervals (CIs) will be reported for treatment difference between apremilast and placebo arms. Multiplicity adjustment will be specified in the next section.

The continuous endpoints will be analyzed using a mixed-effect model for repeated measures (MMRM) as the primary method. The MMRM model will use the change from baseline as the response variable and include treatment group, visit time, treatment-by-time interaction, and stratification factor as fixed effects, and the baseline value as a covariate. An unstructured covariance matrix will be used to model the correlation among repeated measurements. The Kenward-Roger adjustment will be used with restricted maximum likelihood (REML) to make proper statistical inference. Within-group least-squares (LS) means and the associated standard errors (SEs) and two-sided 95% CIs, treatment differences in LS means and the associated two-sided 95% CIs and two-sided p-values will be derived from the MMRM model. A sensitivity analysis will be conducted using the analysis of covariance (ANCOVA) model with treatment and stratification factor as the fixed effects, the baseline value as the covariate and the LOCF method to impute the missing data.

The binary endpoints will be analyzed similarly as the primary endpoint using the CMH test adjusting for the stratification factor at randomization. The two-sided p-values from the CMH test, the adjusted treatment difference in proportion using the weighted average of the treatment differences across the strata with the CMH weights, along with the associated two-sided 95% CIs using a normal approximation to the weighted average will be provided. Missing values at Week 16 will be imputed using the multiple imputation (MI) method (SAS Institute Inc., 2011) based on similar subjects who remained in the study as the primary method. Sensitivity analysis will be conducted to account for missing data using the last observation carried forward (LOCF) method and the non-responder imputation (NRI) method.

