2. INTRODUCTION

This statistical analysis plan (SAP) describes the analyses and data presentations for Celgene's protocol CC-10004-PSOR-022, "A phase 3, multi-center, randomized, double-blind, placebo-controlled study to evaluate the efficacy and safety of apremilast (CC-10004) in subjects with mild to moderate plaque psoriasis".

After all subjects have completed or have been discontinued from the Double-blind Placebo-controlled Phase (Weeks 0 to 16), a Week 16 database restriction will be performed; the primary data analysis will be conducted and a Week 16 Clinical Study Report will be generated. No interim analysis is planned prior to this primary data analysis. At the end of the study, after all subjects have completed or have been discontinued from the Apremilast Extension Phase (Weeks 16 to 32) and the Observational Follow-up Phase, the final database lock and analysis will be performed and the final Clinical Study Report (CSR) will be generated.

No pharmacokinetic (PK) analyses will be done for this study. The details of the pharmacodynamic (PD) analyses except biomarker analysis for plasma proteins assessments will be specified in a separate PD analysis plan.

This SAP provides a more technical and detailed elaboration of the statistical analyses as outlined and/or specified in the study protocol amendment 2 dated 21Nov2018. The SAP will be finalized and signed prior to the unblinding of the Week 16 database. All statistical analyses detailed in this SAP will be conducted using SAS® Version 9.3 or higher.

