4.2.2. Secondary Endpoints

- BSA-75: Proportion of subjects who improved ≥ 75% in BSA (BSA-75) from baseline at Week 16
- BSA: Change from baseline in affected BSA at Week 16
- PASI: Change from baseline in total PASI score at Week 16
- BSA ≤ 3%: Proportion of subjects who achieved BSA ≤ 3% for subjects with baseline BSA > 3% at Week 16
- Itch NRS: Proportion of subjects with ≥4-point reduction (improvement) from baseline in the whole body itch NRS score at Week 16, among subjects with baseline whole body itch NRS ≥ 4
- ScPGA: Proportion of subjects with ScPGA score of clear (0) or almost clear (1) with at least a 2-point reduction from baseline at Week 16, among subjects with baseline ScPGA score ≥ 2
- DLQI: Change from baseline in DLQI total score at Week 16

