4.4. Sample Size Determination

The sample size estimation is based on the results of the Phase 3 and 4 studies with apremilast. With a total of approximately 574 subjects and a randomization ratio of 1:1, the study will randomize approximately 287 subjects to apremilast 30 mg BID and 287 subjects to placebo. This sample size will provide more than 90% power to detect a 15% difference between the two treatment groups for the primary endpoint at a two-sided significance level of 0.05. The calculation is based on a chi-square test assuming 15% response rate for placebo and adjusting for a 20% dropout rate.

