6.2. Multiplicity Adjustment

The primary and secondary efficacy endpoints will be hierarchically ranked for testing to control the overall type I error rate in claiming statistical significance at the two-sided 0.05 significance level. Specifically, for the primary efficacy endpoint (sPGA response at Week 16), if the two-sided p-value from the comparison between apremilast arm and placebo arm is below 0.05, the outcome will be considered statistically significant and apremilast will be declared effective. For any secondary endpoint, statistical significance will be claimed only if its two-sided p-value is below 0.05 and tests for the primary endpoint and all previous secondary endpoints are significant at the two-sided 0.05 level. The proposed test sequence for the primary and secondary efficacy endpoints is listed as the following:

- Proportion of subjects with an sPGA score of clear (0) or almost clear (1) with at least a 2-point reduction from baseline at Week 16
- Proportion of subjects who improved $\geq 75\%$ in BSA (BSA-75) from baseline at Week 16
- Change from baseline in affected BSA at Week 16
- Change from baseline in total PASI score at Week 16
- Proportion of subjects who achieved BSA ≤ 3% for subjects with baseline BSA > 3% at Week 16
- Proportion of subjects with ≥4-point reduction (improvement) from baseline in the whole body itch NRS score at Week 16, among subjects with baseline whole body itch NRS ≥ 4

- Proportion of subjects with ScPGA score of clear (0) or almost clear (1) with at least a 2-point reduction from baseline at Week 16, among subjects with baseline ScPGA score ≥2
- Change from baseline in DLQI total score at Week 16

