6.4.2. Continuous Variables

The continuous variables for secondary endpoints include the following:

- Change from baseline in affected BSA at Week 16
- Change from baseline in total PASI score at Week 16
- Change from baseline in DLQI total score at Week 16

The continuous efficacy endpoints will be analyzed based on the ITT population using a mixed-effect model for repeated measures (MMRM) as the primary method. The MMRM model will use the change from baseline as the response variable and include treatment group, visit time, treatment-by-time interaction, and stratification factor as fixed effects, and the baseline value as a covariate. An unstructured covariance matrix will be used to model the correlation among repeated measurements. The Kenward-Roger adjustment will be used with restricted maximum likelihood (REML) to make proper statistical inference. Within-group least-squares (LS) means and the associated SEs and 2-sided 95% CIs, treatment differences in LS means and the associated 2-sided 95% CIs and 2-sided p-values will be derived from the MMRM model.

The continuous efficacy endpoints will also be analyzed based on the baseline sPGA categories (sPGA = 2 and sPGA =3) using the similar analysis method specified for the ITT population. For the subjects with baseline sPGA = 2 (mild psoriasis) and sPGA = 3 (moderate psoriasis), the MMRM model will use the change from baseline as the response variable and include treatment group, visit time, and treatment-by-time interaction as fixed effects, and the baseline value as a covariate.

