6.6. Subgroup Analysis

Subgroup analysis will be carried out for sPGA response at Week 16 in the Placebo-controlled Phase based upon baseline demographics and disease characteristics. Summary and analysis will be based on ITT population and missing values will be imputed using MI method. Treatment difference of response rates will be reported with two-sided 95% CI.

Forest plots for the treatment differences in proportions by subgroup will be provided.

The following subgroup variables will be used:

- Baseline sPGA score: 2 (mild), 3 (moderate)
- Sex (Male, Female)
- Race (White, Non-white)
- Age category (<65 years, ≥ 65 years)
- Alcohol usage (Yes, No)
- Tobacco usage (Current user, Past user, Never used)
- Baseline weight category $< 70, \ge 70$ to $< 85, \ge 85$ to $< 100, \ge 100$ kg)
- Baseline BMI category $< 25, \ge 25 \text{ to } < 30, \ge 30 \text{ to } < 35, \ge 35 \text{ to } < 40, \ge 40 \text{ kg/m}^2$
- Duration of plaque psoriasis categories ($< 10, \ge 10 \text{ to } < 20, \ge 20 \text{ years}$)

- Geographical region (USA, Canada)
- Baseline PASI score category ($\leq 7, > 7$)
- Baseline BSA (%) category ($\leq 5, \geq 5$)
- Prior conventional systemic therapies (Used or Never used)
- Prior phototherapies (Used or Never used)

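### The CMH test for BSA ≤ 3% adjusts for sPGA only; adding one prespecified baseline BSA cut would narrow its confidence interval at little cost

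*SAP*

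**What the plan says.** SAP 4.2.2 defines the endpoint as "Proportion of subjects who achieved BSA ≤ 3% for subjects with baseline BSA > 3% at Week 16". Its analysis is in SAP 6.4.1, where for all four binary secondary endpoints "the treatment difference between apremilast arm and placebo arm will be compared using CMH test adjusting for the stratification factor at randomization". The reported estimate is the difference in proportions averaged over the same strata with CMH weights. Protocol 9.6.1.2 agrees: "The binary endpoints will be analyzed similarly as the primary endpoint using the CMH test adjusting for the stratification factor at randomization". SAP 4.3 gives one randomisation factor, baseline sPGA (mild 2, about 30%; moderate 3, about 70%).

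Three other places bear on the point:

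- Protocol 4.2, criterion 5b, admits subjects with baseline BSA from 2% to 15%.
- The MMRM for change in BSA (SAP 6.4.2) includes "visit time, treatment-by-time interaction, and stratification factor as fixed effects, and the baseline value as a covariate", so baseline BSA is adjusted for there.
- SAP 6.6 lists a "Baseline BSA (%) category" split at 5%, but only for subgroup analysis of the sPGA response. SAP 8.2 uses the same split for baseline tables.

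BSA ≤ 3% is fifth in the fixed sequence of SAP 6.2. A secondary endpoint can be claimed only if its own p-value is below 0.05 and "tests for the primary endpoint and all previous secondary endpoints are significant at the two-sided 0.05 level". Itch NRS, ScPGA and DLQI come after it.

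**The concern.** The endpoint is an absolute threshold, so how far a subject must improve is set by where that subject starts. Someone starting just above 3% needs almost no change; someone starting at 15% must lose four fifths of the affected area. Baseline BSA is therefore strongly prognostic by arithmetic, whatever the drug does.

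For the primary endpoint the chosen stratification does this work: a subject at sPGA 2 must reach 0 while one at 3 may reach 1, and the test is stratified by exactly that. For BSA ≤ 3% the same factor does not, because sPGA (Protocol 6.4, Appendix B) grades erythema, scaling and plaque elevation rather than extent.

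What is at stake is precision. The variation in success rates between subjects with small and large baseline BSA stays in the error term, so the interval for the treatment difference is wider than it needs to be. Power at position 5, which also gates the itch, scalp and DLQI tests, is somewhat lower than the same data could give.

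**Working it through.** **1. The plan's own figure.** Neither document gives power or precision for this endpoint. The only stated figure is for the primary endpoint (SAP 4.4): more than 90% power for 15% versus 30%, "at a two-sided significance level of 0.05", with 287 per arm and 20% dropout. With 287 × 0.8 = 229.6, take n = 229 per arm:

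z = [0.15·√229 − 1.96·√(2 × 0.225 × 0.775)] / √(0.15 × 0.85 + 0.30 × 0.70) = (2.270 − 1.157) / 0.581 = 1.915, so power is 97.2%. The statement is true, but says nothing about BSA ≤ 3%.

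**2. Reduction needed, by baseline BSA.** Formula: (baseline − 3) / baseline.

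- At 5%: (5 − 3)/5 = 40%.
- At 15%: (15 − 3)/15 = 80%.

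A cut at 5% therefore separates subjects who need at most 40% from those who need more than 40% and up to 80%.

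**3. Why a cut helps: hand check with assumed rates.** Take two equal halves by baseline BSA, with success 45%/15% on placebo and 65%/30% on apremilast, ignoring sPGA. The risk difference is the same either way: 47.5% − 30% = 17.5 points unstratified, and (20 + 15)/2 = 17.5 points stratified. The variance per subject is not:

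- Unstratified: 0.30 × 0.70 + 0.475 × 0.525 = 0.459375.
- Stratified: (0.2475 + 0.1275)/2 + (0.2275 + 0.21)/2 = 0.1875 + 0.21875 = 0.40625.

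SE ratio = √(0.40625/0.459375) = 0.94, an interval 6% narrower.

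**4. Simulations.** Each compares CMH by sPGA with CMH by sPGA × baseline BSA (≤ 5%, > 5%). All distributional inputs are assumptions.

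- *Set A:* 36 scenarios × 2,000 replicates. 459 (574 × 0.8) or 574 subjects with data; lognormal baseline BSA limited to 2–15%, median 5.5 (log-SD 0.50) or 6.5 (log-SD 0.55); 70% sPGA 3; mean log ratio of Week 16 to baseline BSA −0.15 on placebo and −0.30, −0.40 or −0.55 on apremilast; log-SD of the ratio 0.5, 0.7 or 0.9.
- *Set B:* 480 subjects with baseline BSA > 3% (300 also tried); uniform or right-skewed baseline on 3–15%; log-ratio SD 0.5, 0.8 or 1.2; correlation of sPGA with log BSA 0 or 0.4; no missing data.

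| | Set A | Set B |
|---|---|---|
| SE ratio, with cut / without | 0.909–0.967 | 0.881–0.987 |
| CI narrower by | 3.3–9.1% | about 1–12% |
| Equivalent extra subjects (1/ratio² − 1) | 7–21% | 3–29% |
| Power gain | 0–6.5 points, median 2.4 | modest effect: 56.5→60.4%, 64.1→67.4%, 70.7→73.0% |

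In Set A, placebo success was 39–44% at baseline BSA ≤ 5% and 8–21% above 5%. In Set B, with skewed baseline and SD 0.8, cuts at 4, 5, 7 and 10% gave SE ratios of about 0.97, 0.96, 0.96 and 0.98, so the choice of cut is not critical.

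**5. Type I error.** Set A null (8 scenarios × 3,000 replicates): 4.8% as planned, 4.7% with the cut. Set B null (4,000 replicates each): 4.2–4.8% as planned, 4.6–4.9% with the cut.

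**6. Missing data.** 574 randomised, 20% missing at random, multiple imputation (M = 20 rather than the plan's 50), 800 replicates: SE ratios 0.931, 0.957 and 0.971, so 2.9–6.9% narrower. Null rejection (1,500 replicates): 3.8% versus 3.5%. Power moved from 44.9 to 53.0%, 75.9 to 79.9% and 56.4 to 59.5%. The first gain is probably inflated by simulation noise: an SE ratio of 0.931 applied to 44.9% predicts about 50.3%.

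**7. Effect on the sequence (Set A).** The chance of passing BSA-75, BSA change and this test together changed by −0.2 to +2.5 points, median 0.7. Two examples with 459 subjects, median 5.5 and log-SD 0.7:

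- Apremilast mean −0.40: power for this test 67.0→72.2%, joint 33.8→36.2%.
- Apremilast mean −0.55: power 97.5→98.6%, joint 88.2→88.8%.

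The joint figure used ANCOVA in place of the MMRM and left out the sPGA and PASI tests, which can only lower the chance of reaching position 5.

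**The case against.** The best case for leaving the plan alone is that nothing in it is wrong. The SAP follows the protocol, analyses by the factor used at randomisation, and applies one rule to the primary and all binary secondary endpoints. The gain in the testing sequence is small, and where power is already above 97% it adds at most 1.1 points. Against that stand a departure from the protocol's test, a cut-point to defend and two more strata. All of this is true, and it is why the point concerns efficiency only.

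A second objection is selectivity. Other responder endpoints also depend on baseline: an itch score of 4 must fall to 0 while 10 need only fall to 6, and a ScPGA of 2 must reach 0 while 3 or 4 may reach 1. That is fair. The gain for those endpoints was not calculated here, and leaving them as planned does not make the change to BSA ≤ 3% unsound.

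Third, the size depends wholly on assumptions, and the lower end of the wider range, about 1%, is close to nothing. This stands as a limit on magnitude. The direction did not change: the SE ratio was below 1 in every scenario of both sets, including those where sPGA was correlated with BSA.

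Sparse strata are a weaker worry. In Set A the smallest stratum averaged 17–28 subjects per arm and never fell below 5, the minimum cell size SAP 6.7 itself uses when it adds pooled site as a stratum.

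**Conclusion.** The point holds as an efficiency improvement. The planned test keeps its type I error and estimates the right difference, but it ignores a baseline value that determines how hard the endpoint is to reach. One prespecified cut at 5% would narrow the interval by roughly 3–9% under the central assumptions and 1–12% under wider ones. The gain is largest when baseline BSA is widely spread and percentage change varies little between subjects, and smallest when percentage change varies a great deal. Power for this single test rises by a few points at moderate effects; the sequence as a whole barely moves.

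These sizes rest on assumed BSA distributions, response variability and effect sizes, because the documents give none for this endpoint. The change is worth making because it is cheap and validity is unaffected. It has to be prespecified: stratifying this way after unblinding would look data-driven.

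**What to change.** Add to SAP 6.4.1, for this endpoint only:

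> BSA ≤ 3% at Week 16 among subjects with baseline BSA > 3% will be analysed with the CMH test and the CMH-weighted difference stratified by randomisation sPGA (2, 3) and baseline BSA (> 3% to ≤ 5%, > 5%). The same strata apply to each imputed data set and to the NRI analysis. The CMH test stratified by sPGA alone is supportive. If a stratum has no subject in one arm, the two BSA categories are pooled within that sPGA level.

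State on which side exactly 5.0% falls. The wording above puts it in the lower category; the categories in SAP 6.6 and 8.2 appear with 5 on both sides, which may be a conversion fault but should be settled. The chi-squared analyses within sPGA 2 and sPGA 3 can stay as they are.

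Timing is set by the SAP's own rule (section 2): "The SAP will be finalized and signed prior to the unblinding of the Week 16 database". Record the change as a departure from Protocol 9.6.1.2 before then, with a protocol amendment if the sponsor's procedures require one.

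The cost is one SAP paragraph and some programming, with no new data. The downsides are the documented departure, a cut-point fixed in advance, four strata instead of two, and one binary endpoint analysed differently from the other three.

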6.4.2. Continuous Variables

The continuous variables for secondary endpoints include the following:

- Change from baseline in affected BSA at Week 16
- Change from baseline in total PASI score at Week 16
- Change from baseline in DLQI total score at Week 16

The continuous efficacy endpoints will be analyzed based on the ITT population using a mixed-effect model for repeated measures (MMRM) as the primary method. The MMRM model will use the change from baseline as the response variable and include treatment group, visit time, treatment-by-time interaction, and stratification factor as fixed effects, and the baseline value as a covariate. An unstructured covariance matrix will be used to model the correlation among repeated measurements. The Kenward-Roger adjustment will be used with restricted maximum likelihood (REML) to make proper statistical inference. Within-group least-squares (LS) means and the associated SEs and 2-sided 95% CIs, treatment differences in LS means and the associated 2-sided 95% CIs and 2-sided p-values will be derived from the MMRM model.

The continuous efficacy endpoints will also be analyzed based on the baseline sPGA categories (sPGA = 2 and sPGA =3) using the similar analysis method specified for the ITT population. For the subjects with baseline sPGA = 2 (mild psoriasis) and sPGA = 3 (moderate psoriasis), the MMRM model will use the change from baseline as the response variable and include treatment group, visit time, and treatment-by-time interaction as fixed effects, and the baseline value as a covariate.

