#### 4.2. Inclusion Criteria

Subjects must satisfy the following criteria to be enrolled in the study:

- 1. Subject must be male or female, ≥18 years of age at the time of signing the informed consent form (ICF).
- 2. Subject must understand and voluntarily sign an ICF prior to any study-related assessments / procedures being conducted.
- 3. Subject is willing and able to adhere to the study visit schedule and other protocol requirements.
- 4. Subject must have a diagnosis of chronic plaque psoriasis for at least 6 months prior to signing the ICF.
- 5. Subject must have a diagnosis of mild to moderate plaque psoriasis at both Screening and Baseline as defined by:
  - a. sPGA score of 2-3 (mild to moderate)
  - b. BSA 2-15%
  - c. PASI score 2-15
- 6. Subject must be inadequately controlled with, or intolerant of at least one topical therapy (including topical corticosteroids, topical retinoids or vitamin D analog preparations, calcipotriene and betamethasone dipropionate ointment or foam, tacrolimus, pimecrolimus, or anthralin/dithranol) for the treatment of psoriasis at both Screening and Baseline.
- 7. Subject has not had prior exposure to biologics for the treatment of psoriatic arthritis, psoriasis, or any other indication that could impact the assessment of psoriasis.
- 8. Subject must be in good health (except for psoriasis) as judged by the investigator, based on medical history, physical examination, clinical laboratories, and urinalysis.
- 9. Subject must meet the following laboratory criteria:
  - a. White blood cell count  $\ge 3000/\text{mm}^3 \ (\ge 3.0 \times 10^9/\text{L})$  and  $< 14,000/\text{mm}^3 \ (< 14 \times 10^9/\text{L})$
  - b. Platelet count  $> 100.000/\mu L$  ( $> 100 \times 109/L$ )
  - c. Serum creatinine  $\leq 1.5 \text{ mg/dL}$  ( $\leq 132.6 \mu \text{mol/L}$ )
  - d. Aspartate aminotransferase (AST) (serum glutamic oxaloacetic transaminase [SGOT]) and alanine aminotransferase (ALT) (serum glutamic pyruvic transaminase [SGPT])  $\leq 2$  x upper limit of normal (ULN)
  - e. Total bilirubin  $\leq 2 \text{ mg/dL } (34 \mu\text{mol/L})$

10. Females of childbearing potential (FCBP) must have a negative pregnancy test at Screening and Baseline. While on investigational product and for at least 28 days after taking the last dose of investigational product, FCBP who engage in activity in which conception is possible must use one of the approved contraceptive options described below:

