5.4. Time Points

Time points in all analyses are based on the remapped visits/study weeks using the following visit mapping algorithm, which may or may not be the same as the visits/study weeks as recorded in the database.

All visit-based data, except for those with the recorded visit being a follow-up visit, will be assigned to analysis visits based on study day (the date of assessment/collection relative to the reference date) and the defined analysis visit windows (Table 2), rather than the recorded visit. The only exception is that data with the recorded visit being a follow-up visit will be assigned to the analysis visit corresponding to the follow-up visit.

Table 2: Table for Visit Mapping

Analysis Visit	Target Day	Visit Window
Week 0 (Baseline)	1	≤1
Placebo-controlled Phase		
Week 2	15	2 – 21
Week 4	29	22 – 42
Week 8	57	43 – 70
Week 12	85	71 – 98
Week 16	113	99 – End of Phase
Apremilast Extension Phase		
Week 20	141	Start of Phase – 154
Week 24	169	155 – 196
Week 32	225	197 – End of Phase

Note: Target day and visit window are relative to the date of Visit 2/Week 0 (Day 1) randomization date. For efficacy and safety analysis, definitions for start or end dates for a phase or period are specified in Section 5.1 and Baselines are specified in Section 5.3.

Time points in the analyses or summaries of efficacy data over time include the scheduled study weeks per protocol, the end of a study phase, and the observational follow-up visit when applicable. It is possible that multiple assessment values will fall into the same visit window. The following rule may be used to select the unique value for that analysis visit:

- 1. Among all assessments in the same visit window for the analysis visit, select the value with the assessment date closest to the target day of the analysis visit;
- 2. If the relative days from 2 assessments are equally close to, but on different sides of the target day, then the latter assessment will be used for that analysis visit;

3. If multiple assessments are available on the same relative day, the duplicated values will be suppressed; otherwise, the highest value of these assessments will be used for that relative day.

For the Apremilast-exposure Period, the scheduled study weeks for placebo subjects who are treated with apremilast 30 mg BID at Week 16/Visit 7 are shown below for summaries of safety data (laboratory parameters, vital signs, etc) over time.

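### The MMRM for BSA, PASI and DLQI change fits one baseline slope for all visits; adding baseline-by-visit is a near-free precision gain at Week 16 for BSA and PASI

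*SAP*

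**What the plan says.** SAP 6.4.2 analyses Week 16 change in BSA, PASI and DLQI by MMRM with unstructured covariance, REML and Kenward-Roger. The model will "include treatment group, visit time, treatment-by-time interaction, and stratification factor as fixed effects, and the baseline value as a covariate". Protocol 9.6.1.2 and the Protocol Summary specify the same model. The separate sPGA=2 and sPGA=3 models drop the stratum and "include treatment group, visit time, and treatment-by-time interaction as fixed effects, and the baseline value as a covariate". None of them has a baseline-by-visit term.

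SAP 6.4.2 does not list the visits in the model. Under SAP 5.4, data "will be assigned to analysis visits based on study day", and the Placebo-controlled Phase has Weeks 2, 4, 8, 12 and 16. Protocol Table 3 schedules all three measures at each of these, so I take five post-baseline visits.

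The Protocol also has a supporting analysis: "A sensitivity analysis will be conducted using the analysis of covariance (ANCOVA) model with treatment and stratification factor as the fixed effects", with LOCF. SAP 6.4.2 does not repeat it.

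**The concern.** Protocol 4.2 admits BSA of 2-15% and "PASI score 2-15". Neither measure can go below 0, so a subject entering at 2 can improve by at most 2 points and one entering at 15 by up to 15. As response accumulates, the regression of change on baseline should steepen. A slope shared across visits is pulled towards the earlier ones, and the unexplained baseline effect stays in the Week 16 residual variance. DLQI uses the same model but has no entry range, so I do not argue drift for it.

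What is at stake is precision in the confirmatory test. BSA change is third and PASI change fourth in the fixed sequence of SAP 6.2, where a claim requires that "tests for the primary endpoint and all previous secondary endpoints are significant at the two-sided 0.05 level". A narrow miss on BSA change would block the five endpoints after it: PASI change, BSA of 3% or less, itch, ScPGA and DLQI. Power is stated only for the primary endpoint, so the documents do not show how much BSA and PASI change have to spare.

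**Working it through.** **The plan's own figure.** SAP 4.4 claims more than 90% power for 15% versus 30% response with 287 per arm, "adjusting for a 20% dropout rate". With 287 × 0.8 ≈ 230 evaluable per arm:

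Φ[(0.15 − 1.96√(2 × 0.225 × 0.775/230)) / √((0.15 × 0.85 + 0.30 × 0.70)/230)] = Φ(1.92) ≈ 97.3%

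The claim is correct. There is no counterpart for the MMRM endpoints.

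**Formula (complete data, large sample).** Let β be the vector of true slopes by visit, S the residual covariance and SD_B the baseline SD. The shared-slope model estimates

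b = (1′S⁻¹β) / (1′S⁻¹1)

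and the Week 16 standard error is inflated, relative to the interaction model, by

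R = √[1 + (β₁₆ − b)² SD_B² / σ₁₆²]

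**Inputs.** From the documents: N=574, five visits, 20% dropout, entry range 2-15. Assumed: baseline mean 7 and SD 3, truncated to 2-15, giving SD_B = 2.66; σ₁₆ = 3; residual correlation 0.5-0.7; residual SD constant at 3 or growing from 2 to 3; slope linear in time from Week 2 to Week 16.

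**Worked case: slope -0.20 to -0.4, constant SD, equal correlation.** Here b is the plain mean of the five slopes. The fractions of the Week 2 to Week 16 interval are 0, 2/14, 6/14, 10/14 and 1, with mean 0.457. So b = −0.20 − 0.2 × 0.457 = −0.291, and β₁₆ − b = −0.109. Then R = √[1 + (0.109 × 2.66/3)²] ≈ 1.005.

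**All paths.** The second column repeats this hand calculation. The third adds 20% monotone random dropout and spans both SD patterns and both correlations. Power is Φ(3.24/R − 1.96).

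| Slope, Week 2 to Week 16 | SE increase, worked case | SE increase, 20% dropout | 90% power becomes |
|---|---|---|---|
| constant | 0% | 0% | 90% |
| -0.05 to -0.2 | 0.3% | 0.3-1.1% | 89.4-89.8% |
| -0.05 to -0.4 | 1.4% | 1.9-5.7% | 86.6-88.9% |
| -0.05 to -0.6 | 3.4% | 4.7-13.4% | 81.6-87.2% |
| -0.20 to -0.4 | 0.5% | 0.6-1.9% | 88.9-89.6% |
| -0.20 to -0.6 | 1.8% | 2.5-7.4% | 85.6-88.5% |

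The -0.20 start allows for a slope already present at Week 2, for example from regression to the mean after the entry limits. The -0.6 paths are upper bounds. An endpoint with 99% power keeps at least 96.6% in every case.

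**In subjects.** The equivalent loss is 1 − 1/R². For -0.20 to -0.4 it is 1.2-3.7%, about 7-21 of 574. For -0.05 to -0.4 it is 3.7-10.4%, about 21-60.

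**Simulation.** REML fits of both models to the same simulated trials (150 per setting) gave matching ratios, for example 1.0191-1.0569 for -0.05 to -0.4 and 1.0060-1.0188 for -0.20 to -0.4. In 1,500 trials with growing SD, correlation 0.7 and 90.0% power under the interaction model, the shared slope gave 85.9% and 88.2% for these two paths. With no true effect its mean error was 0.003 and 0.002 (Monte Carlo error 0.007), so there is no sign of bias.

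**A different mechanism.** When follow-up values were simulated as proportional to baseline, bounded at 0, with baseline SD about 2.5-3.5, the interaction lowered the Week 16 standard error by 0.6-3.3%. One DLQI-like scenario gave 0.3%.

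**The case against.** The planned model is valid, prespecified and identical in Protocol and SAP, so this can be called preference. Apart from N, the visits, the entry range and the dropout rate (set for the binary primary endpoint), every input is assumed. The proportional-response scenarios put the gain at about 1-3% of the standard error, well below the top of the table.

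Steep slopes also sit awkwardly with 90% power. With SD 3 and 230 per arm, 90% power corresponds to a difference of 3.24 × 3 × √(2/230) ≈ 0.91 points, 13% of a baseline mean of 7. If the slope reflects proportional response, a Week 16 slope of -0.6 would then mean mean reductions of roughly 53% on placebo and 67% on apremilast. A wider gap between arms would put power well above 90%.

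The gatekeeping harm needs sPGA response and BSA-75 to succeed and BSA change then to miss narrowly. The Protocol's ANCOVA already fits its own Week 16 slope.

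Most of this stands as a limit on size: the likely gain is small and the -0.6 paths should not be read as expected. It does not remove the point. The ANCOVA is only a sensitivity analysis and recovers no precision in the confirmatory test. BSA-75 measures relative change, so its success does not guarantee success on absolute change.

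**Conclusion.** The point holds as a suggestion to consider. The plan fits one baseline slope across five visits while testing only the last, and the entry range and floor at 0 make a steepening slope plausible for BSA and PASI. A realistic gain is roughly 1-3% of the Week 16 standard error, up to about 6% if the slope moves from near zero to -0.4, and nil if it is constant. These figures rest on the assumed SDs, correlations and slope paths.

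With complete data, random dropout, or baseline-linked dropout equal in both arms, the planned estimate is valid. Bias would need dropout to depend on baseline differently by arm, which nothing in the documents shows. If BSA and PASI change are very highly powered, the practical benefit is small.

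**What to change.** Before the Week 16 unblinding, add the baseline-value-by-visit interaction to the ITT model and to the sPGA=2 and sPGA=3 models in SAP 6.4.2, keeping every other term, the covariance structure, REML and Kenward-Roger. Apply it to DLQI too, so that the three endpoints share one model. Align Protocol 9.6.1.2 and the Protocol Summary, or record the departure in the SAP, and state there whether the ANCOVA/LOCF analysis is kept. Stratum-by-visit follows the same logic but gains only 0.1-1.4% of the standard error for a stratum effect of 0.5-1.0 points emerging by Week 16, so it is optional.

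The cost is one model term with 4 degrees of freedom and a wording change. If slopes are constant, the Week 16 standard error rises by about 0.04% at N=574 and at N=402 (sPGA=3, 70% of 574), and by about 0.15% at N=172 (sPGA=2, 30% of 574). No extra data are needed and patients are not affected.
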